10.3.2.2 Analysis of the primary efficacy variables

This section was changed in Amendment 2, see Section 15.1 for details.

For both primary efficacy variables, it is planned to perform a test for a dose-response signal, respectively, under the assumption of a nearly monotone dose-response relationship in the dose range considered. The MCP-Mod method (46) combining multiple comparison procedures (MCP) principles with modeling techniques will be used for the primary statistical analysis of the primary efficacy variables. This method allows the flexibility of modeling for dose estimation, while preserving the robustness to model misspecification associated with MCP procedures.

Two primary variables have been defined to better evaluate multiple dimensions of the treatment effect, thereby adding a source of multiplicity. The overall outcome of the primary efficacy analysis will be considered positive if at least one of the two null hypotheses related to the primary efficacy variables can be rejected. The Hochberg (step-up) procedure will be applied to control the family-wise error rate (FWER):

Consider the null hypotheses for LVEF, $H_{0,LVEF}$, and for NT-proBNP, $H_{0,NT-proBNP}$, and their associated raw p-values p_{LVEF} and $p_{NT-proBNP}$. The Hochberg test is performed using the following steps:

1. If $\max(p_{LVEF}, p_{NT-proBNP}) \leq \alpha = 0.05$, both null hypotheses $H_{0,LVEF}$ and $H_{0,NT-proBNP}$ will be rejected and the procedure stops.
2. If $\max(p_{LVEF}, p_{NT-proBNP}) > \alpha = 0.05$ and $\min(p_{LVEF}, p_{NT-proBNP}) \leq \alpha/2 = 0.025$, the null hypothesis related to the larger p-value $\max(p_{LVEF}, p_{NT-proBNP})$ will be accepted and the null hypothesis related to the smaller p-value $\min(p_{LVEF}, p_{NT-proBNP})$ will be rejected.
3. Otherwise, both null hypotheses $H_{0,LVEF}$ and $H_{0,NT-proBNP}$ will be accepted.

Assumptions

Five active doses of neladenoson bialanate will be used in this study: 5 mg, 10 mg, 20 mg, 30 mg, and 40 mg, as well as a placebo arm corresponding to a 0 mg dose.

The measurements of the primary efficacy variables are assumed to be normally distributed with the same standard deviation σ and independent between patients, respectively.

LVEF: The following assumptions were made for the absolute change from baseline in LVEF over 20 weeks:

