- the expected mean effect under the placebo dose is conservatively assumed as an absolute increase from baseline of up to $\Delta = 2\%$ with a standard deviation of $\sigma = 7\%$
- while the maximum observable mean effect under neladenoson bialanate within the dose range considered is assumed as an absolute increase of $\Delta = 5\%$ with a standard deviation of $\sigma = 7\%$.

This results in an expected maximum effect size of $(5-2)/7 = 3/7 = 0.43$ under conservative assumptions. Note that the threshold of clinical relevance is an absolute difference of 3% in the change from baseline over the placebo control group.

NT-proBNP: The following assumptions were made for the absolute change from baseline in the log-transformed NT-proBNP over 20 weeks:

- the expected mean effect under the placebo dose is assumed as an absolute decrease from baseline of $-0.105 \log(\text{pg/mL})$ with a standard deviation of $\sigma = 0.85 \log(\text{pg/mL})$, which is equivalent to a 10% relative reduction from a mean of 2,500 pg/mL at baseline.
- while the maximum observable mean effect under neladenoson bialanate within the dose range considered is assumed as an absolute decrease from baseline of $-0.357 \log(\text{pg/mL})$ with a standard deviation of $\sigma = 0.85 \log(\text{pg/mL})$, which is equivalent to a 30% relative reduction from a mean of 2,500 pg/mL at baseline.

It is assumed that the respective primary response efficacy variable, denoted as Y , is observed for the 6 parallel groups corresponding to doses levels: (placebo =) $d_1 < d_2 < \dots < d_k$, where $k = 6$.

For patient j within treatment group i the response can then be described by the following model:

$$Y_{ij} = f(d, \boldsymbol{\theta}) + \varepsilon_{ij}, \quad \varepsilon_{ij} \sim N(0, \sigma^2), \quad i = 1, \dots, k, \quad j = 1, \dots, n_i,$$

[figure not shown]
where $f(\cdot)$ is parameterized by a vector of parameters $\boldsymbol{\theta}$ and ε_{ij} is the error term.

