10.4 Determination of sample size

In the first step, this combined proof-of-concept and Phase IIb dose-finding study has been powered for the detection of a dose response signal in the primary efficacy variable change in LVEF.

The sample size for the primary efficacy variable change in LVEF was evaluated under the assumptions described in Section 10.3.2.2 and a type I error level = 5% with the aim to achieve at least 80% power for the one-sided primary multiple contrast test. The overall randomization ratio was assumed to be 3:1:2:2:2:2 for doses 0, 5, 10, 20, 30, and 40 mg.

Table 10–2 displays the power for the multiple contrast test in the MCP-Mod approach, used as primary analysis, for the set of specified alternatives.

Table 10–2: Power for multiple contrast test for set of different alternatives

Sample size		Power for alternative based on respective dose-response model (in %)					
Overall	Per group ^a	Linear	Sigmoidal E _{max} 1	Sigmoidal E _{max} 2	E _{max}	Quadratic	Minimum
240	40	73.36	86.24	81.20	82.26	79.97	73.36
252	42	75.26	87.73	82.94	83.94	81.70	75.26
264	44	77.10	89.13	84.58	85.58	83.31	77.10
276	46	78.71	90.30	85.97	86.94	84.70	78.71
288	48	80.31	91.39	87.30	88.25	86.09	80.31
300	50	81.62	92.27	88.42	89.32	87.24	81.62
312	52	82.99	93.15	89.53	90.38	88.39	82.99
324	54	84.25	93.92	90.54	91.37	89.50	84.25
336	56	85.43	94.60	91.45	92.22	90.39	85.43
348	58	86.56	95.22	92.31	93.02	91.28	86.56

^a Number of patients randomized to dose levels 10 mg, 20 mg, 30 mg, and 40 mg of neladenoson bialanate, for placebo sample size per group to be multiplied by 3/2, for dose level 5 mg sample size per group to be divided by 2.

To achieve at least 80% power for the multiple contrast test in the MCP-Mod approach under all different alternatives, a minimum of 48 patients per treatment group (72 patients for the placebo and 24 patients for the 5 mg group) is needed, resulting in an overall sample size of N = 288 patients.

In the second step, the power for the multiple contrast test in the MCP-Mod approach for the absolute change in log-transformed NT-proBNP was estimated, based on the assumptions outlined in Section 10.3.2.2 and a given sample size of $N = 288$. Statistical simulations were used to assess the power of the Hochberg test to reject at least one of the two null hypotheses. It was concluded that an overall sample size of $N = 288$ patients is sufficient to reject at least one of the two primary efficacy hypotheses with a power of about 83%.

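### Table 10-2 gives LVEF power for a stand-alone 5% test; under the planned Hochberg rule the minimum (linear-shape) LVEF power at N = 288 is about 74–76%, and the 83% figure rests on an unstated shape and endpoint correlation

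*Protocol*

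**What the plan says.** Protocol section 10.4 sizes the trial in two steps.

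Step 1 concerns LVEF alone: the study "has been powered for the detection of a dose response signal in the primary efficacy variable change in LVEF", at "a type I error level = 5% with the aim to achieve at least 80% power for the one-sided primary multiple contrast test". Table 10-2 "displays the power for the multiple contrast test in the MCP-Mod approach, used as primary analysis, for the set of specified alternatives". At N = 288 the entries are 80.31% (linear), 91.39% (sigmoidal Emax 1), 87.30% (sigmoidal Emax 2), 88.25% (Emax) and 86.09% (quadratic). The minimum, 80.31%, decides the size: "a minimum of 48 patients per treatment group (72 patients for the placebo and 24 patients for the 5 mg group) is needed" if 80% is to be met whichever shape is true.

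Step 2 brings in NT-proBNP at the same N. From simulations of the Hochberg test, the protocol concludes that 288 "patients is sufficient to reject at least one of the two primary efficacy hypotheses with a power of about 83"%. It adds that this drops below 80% if the NT-proBNP reduction on drug is under 27.5%, against 10% on placebo. It gives neither the dose-response shape nor the correlation between the two endpoints used in the simulation.

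The decision rule is in Protocol 10.3.2.2 and is repeated in SAP 6.2.1.2: "The Hochberg (step-up) procedure will be applied to control the family-wise error rate (FWER"). Both nulls are rejected if the larger p-value is at most 0.05. Otherwise only the smaller p-value can lead to rejection, and it must be at most 0.025. One rejection is enough for a positive trial.

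**The concern.** Step 1 tests LVEF at the full 5%, whereas the decision rule allows LVEF the full 5% only when NT-proBNP is also significant at 5%. Table 10-2 is nevertheless described as the power of the test used in the primary analysis, and the 80% criterion that fixed N = 288 is read from it with a margin of 0.31 points. Any cost from the Hochberg split therefore takes the minimum below 80%.

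The second issue is disclosure. At-least-one power depends on how strongly the two endpoints are correlated within patients, because correlated tests tend to fail together. The protocol shows sensitivity to the NT-proBNP effect size but none to correlation. A reader judging a null LVEF result, or planning from these figures, would credit the design with more power than its rule gives in the least favourable case.

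**Working it through.** **Inputs.** Allocation: "The overall randomization ratio was assumed to be 3:1:2:2:2:2 for doses 0, 5, 10, 20, 30, and 40 mg", so n = 72, 24, 48, 48, 48, 48 at N = 288. LVEF: placebo +2%; "the maximum observable mean effect under neladenoson bialanate within the dose range considered is assumed as an absolute increase of" 5%; SD 7%. NT-proBNP: −0.105 on placebo, −0.357 at most on drug, SD 0.85 on the log scale. Shapes: Protocol Table 10-1. Not in the documents: the correlation ρ between the two changes (positive when the benefits go together); ρ from 0 to 0.5 is assumed.

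**Contrasts.** Optimal contrasts are proportional to nᵢ(μᵢ − μ̄). For the linear shape the weighted mean dose is 4920/288 = 17.08 mg. The products nᵢ(dᵢ − 17.08) are −1230, −290, −340, 140, 620 and 1100. Scaled to unit length they are −0.674, −0.159, −0.186, 0.077, 0.340 and 0.603, which is the linear row of SAP Table 6-2. The other rows agree within 0.001.

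**Signal size, linear shape.** Σnᵢ(dᵢ − d̄)² = 144,600 − 84,050 = 60,550, with square root 246.07. The noncentralities are:
- LVEF: 0.075 × 246.07 / 7 = 2.64
- NT-proBNP: 0.0063 × 246.07 / 0.85 = 1.82

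**Critical values.** For the maximum of five correlated t statistics with 282 df, they are about 1.965 at one-sided 5% and 2.273 at 2.5%.

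**The plan's own figures.** Simulating the maximum contrast at unadjusted 5% gives 80.2 / 91.3 / 87.3 / 88.2 / 86.1%, against 80.31 / 91.39 / 87.30 / 88.25 / 86.09% in Table 10-2. The rows for N = 240 and N = 348 also match. The table is therefore correct as stand-alone LVEF power at 5%.

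**LVEF under Hochberg, linear shape.** P(reject LVEF) = P(p ≤ 0.025) + P(0.025 < p ≤ 0.05 and NT-proBNP p ≤ 0.05). Stand-alone LVEF power is 80.3% at 5% and 70.4% at 2.5%; NT-proBNP power at 5% is 52.5%.
- ρ = 0, both effects as assumed: 70.4 + (80.3 − 70.4) × 0.525 = 75.6%
- ρ = 0, NT-proBNP has no effect: 70.4 + (80.3 − 70.4) × 0.05 = 70.9%

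Joint simulation of both endpoints, with the same shape on each, gives LVEF power (%) under Hochberg at N = 288:

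| Shape | ρ = 0 | ρ = 0.3 | ρ = 0.5 | Table 10-2 |
|---|---|---|---|---|
| Linear | 75.3 | 74.5 | 73.9 | 80.31 |
| Sigmoidal Emax 1 | 89.2 | 88.3 | 87.6 | 91.39 |
| Sigmoidal Emax 2 | 84.1 | 83.1 | 82.4 | 87.30 |
| Emax | 85.2 | 84.3 | 83.6 | 88.25 |
| Quadratic | 82.6 | 81.7 | 81.1 | 86.09 |

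Repeat runs differ by a few tenths of a point; the linear entry at ρ = 0 ranged from 75.3 to 75.7.

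**At least one rejection.** With linear shapes on both endpoints:

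| ρ | 0 | 0.2 | 0.3 | 0.4 | 0.5 |
|---|---|---|---|---|---|
| Power (%) | 83.4 | 80.8 | 79.5 | 78.2 | 76.9 |

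The first entry reproduces the protocol's 83%. In the same setting, a 27.5% NT-proBNP reduction (difference ln(0.90/0.725) = 0.216 instead of 0.252) gives 80.4%, which fits the protocol's stated threshold. The other four shapes give about 83 to 94% over ρ = 0.5 to 0.

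**The case against.** The strongest reply is that section 10.4 declares its basis. Table 10-2 belongs to a first step about LVEF at 5%, Hochberg enters in the second step, and the phrase about primary analysis may refer only to the MCP-Mod contrast test. The protocol nowhere promises 80% LVEF power under Hochberg, and trial success needs only one rejection. All of this stands, and it limits the point to how power is stated. It does not remove the point: the sample size was chosen by a criterion for LVEF that the decision rule does not meet for the shape that set the minimum, and the text does not say so.

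Four stronger readings are tempting, and the documents do not support them.
- A reader might infer that the 83% ignores Hochberg. It does not: the protocol says it was simulated for the Hochberg test with at least one rejection, and it reproduces as such.
- A reader might take 74–76% as LVEF power in general. It applies to the linear shape only; the other four stay above 80% over the assumed correlations.
- A reader might conclude that 83% requires uncorrelated endpoints. That is so only for linear shapes on both endpoints. Other shapes give 83% or more at ρ = 0.5. That the protocol used linear shapes and ρ = 0 is an inference from two matching figures.
- A reader might call the trial undersized or the table miscalculated. The table's arithmetic is right, and LVEF-specific power is not the probability of a positive trial.

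The documents also give no estimate of the correlation. At 0.2 the linear case still has 80.8%, and at 0.3 to 0.5 the shortfall from 80% is about 0.5 to 3 points.

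**Conclusion.** The point holds in limited form. Table 10-2, and the conclusion that 288 evaluable patients give at least 80% for every shape, describe an unadjusted one-sided 5% test of LVEF. Under the planned Hochberg rule the minimum falls to about 74–76%, some 4 to 6 points below the stated 80.31%, and to about 71% if NT-proBNP does not respond. The loss at ρ = 0, with both effects as planned, needs no assumption about correlation beyond the value that reproduces the protocol's own 83%.

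The 83% is the right kind of figure for the trial's success criterion, but it is given without its conditions. For linear shapes it ranges from about 83% (ρ = 0) to 77% (ρ = 0.5), passing below 80% near ρ = 0.3. The upper end is firm; the lower end depends on the assumed correlation range. No change of design or decision rule follows.

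**What to change.** Keep N, and revise the wording of section 10.4.

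1. Label Table 10-2 as stand-alone LVEF power at unadjusted one-sided 5%, and attach the same qualifier to the 80% conclusion.
2. Add LVEF power under Hochberg for all five shapes at N = 288 (minimum about 74–76% for ρ = 0.5 to 0; about 71% with no NT-proBNP effect).
3. State the shape and endpoint correlation behind the 83%, and replace the single figure by a range over shape and correlation (linear: about 77–83% for ρ = 0.5 to 0).
4. Give the 27.5% threshold with the same two conditions.

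The cost is one simulation table and a few sentences. The drawback is that the stated power becomes slightly less favourable. For context only: 80% LVEF power under Hochberg for the linear shape would take about 324 (ρ = 0) to 336 (ρ = 0.5) evaluable patients. Because success needs only one rejection, that alone is not a reason to enlarge the trial.

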3.1 Background

Chronic heart failure (CHF) is a major public health problem characterized by significant mortality, frequent hospitalizations, and poor quality of life, with an overall prevalence that is increasing throughout the world. The European Society of Cardiology (ESC) represents countries with a population of > 900 million, and there are at least 15 million patients with heart failure (HF) in those 51 countries (1). An estimated 5.7 million patients have HF in the United States (US) with increasing prevalence, and the incidence approaches 10 per 1000 population after 65 years of age; the lifetime risk for developing HF is one in five for men and women (2). In developed countries 1–2% of the adult population has HF, with the prevalence rising to $\geq 10\%$ among persons 80 years of age or older (3). HF carries a prognosis comparable to many forms of cancer with a 5-year survival rate of approximately 50% (4), which exceeds that of many cancers (5).

Frequent hospitalizations, along with other direct and indirect costs, also place an enormous financial burden on healthcare systems; more is spent annually in the US for the treatment of HF by Medicare than on any other Medicare-covered condition (6).

The pathophysiology and clinical constellation of patients hospitalized for HF differ substantially from ambulatory patients with HF. Each episode of acute hospitalization for HF occurring annually in up to 30% of HF patients with NYHA class III and IV indicates an unfavorable underlying pathophysiology and prognosis within the course of HF (7). These patients represent an important subpopulation of patients with HF, which is denominated as worsening CHF (WCHF).

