The primary efficacy analysis aims at evaluating the dose-response relationship of the primary and secondary efficacy variables (except for clinical outcomes) for all randomized patients who have remained in the study and adhered to study treatment according to the study protocol until Week 20 (“completers and treatment adherers” analysis). Therefore, the primary analysis will be performed in the per-protocol set, a subset of the FAS comprising “compliant and adherent” patients (as much as possible, defined via validity criteria). To avoid bias, the PPS will also include those “compliant and adherent” patients who are “censored” due to CV death or a hospitalization for HF preventing the assessment of the relevant efficacy endpoints 20 weeks after randomization to take place as planned. It is expected that these are the only patients for whom missing observations need to be considered in the primary analysis. A “worst case” approach will be used, where the missing change from baseline value will be imputed with a multiple of the worst change from baseline value, which is possible given the individual baseline value observed in the respective treatment group, or 0 if the worst change in that treatment group is positive for LVEF / negative for NT-proBNP.

As a sensitivity analysis, a “completers and treatment adherers” only analysis excluding the censored patients in the per-protocol analysis set will be performed. This strategy leads to unbiased estimates only if missing values are “missing completely at random” (MCAR), i.e. the missingness – including missing data due to death – is independent of both observed and unobserved outcomes. This condition is unlikely to hold exactly but rather approximately.

Further sensitivity analyses on the PPS may be performed if the missing data patterns suggest further exploration.

Efficacy analysis using the FAS

The efficacy analysis in the FAS aims at evaluating the dose-response relationship of the primary and secondary efficacy variables for all randomized patients. Efficacy analyses in the FAS will include the following:

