This power would drop to less than 80%, if the relative reduction of NT-proBNP from baseline within the investigated dose range for neladenoson bialanate is $< 27.5\%$ compared to an expected reduction from baseline of 10% under placebo.

Based on these considerations, a total of 384 patients are planned to be randomized to the 6 treatment groups:

- 96 patients are planned to be randomized to placebo (0 mg),
- 64 patients each are planned to be randomized to the dose levels 10 mg, 20 mg, 30 mg, and 40 mg of neladenoson bialanate, and
- 32 patients are planned to be randomized to the dose level 5 mg of neladenoson bialanate.

These numbers already include adequate assumptions on expected drop-out after randomization and invalid or missing data. In the selected population it is expected that only about 75% of all randomized patients, i.e. about 288 patients, will contribute complete data to the primary analysis in the PPS.

All power estimations and simulations were performed with the DoseFinding package in R, version 3.0.2 (2013-09-25).

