6.2.1.2 Primary analysis of primary efficacy variables

Primary analysis will be performed in PPS LVEF and PPS BNP respectively, a subset of the FAS comprising “compliant and adherent” patients (as much as possible, defined via validity criteria). To avoid bias, the PPS LVEF and PPS BNP will also include those “compliant and adherent” patients who are “censored” due to CV death or a hospitalization for HF preventing the assessment of the relevant efficacy endpoints 20 weeks after randomization to take place as planned. For missing post-baseline value due to CV death or study drug/study discontinuation due to HF, a worst case approach (WOV) will be applied. The worst change by treatment group will be calculated. If the worst change in that treatment group is positive for LVEF / negative for NT-proBNP, the worst case in that treatment group is 0. The missing change from baseline value will be imputed with a multiple 1.0 of the median of worst changes from baseline value among all treatment groups. The post-baseline value at week 20 will be calculated accordingly as baseline value + imputed change from baseline. If this imputed post-baseline value for LVEF is < 0% in case of CV death preventing the measurement, then the post-baseline value will be replaced with 0 and the imputed change from baseline will be modified to (- baseline value). Similarly, if the imputed post-baseline value is < 5% in case of a hospitalization for HF and no CV death preventing the measurement, the post-baseline value will be set to 5% and the corresponding imputed change from baseline will be reset to (5 - baseline value).

For both primary efficacy variables, it is planned to perform a test for a dose-response signal, respectively, under the assumption of a nearly monotone dose-response relationship in the dose range considered. The MCP-Mod method (5) combining multiple comparison procedures (MCP) principles with modeling techniques will be used for the primary statistical analysis of the primary efficacy variables. This method allows the flexibility of modeling for dose estimation, while preserving the robustness to model misspecification associated with MCP procedures. The MCP-Mod method will be used based on SAS programs provided (9) and the results may be validated within R (10) with the actual DoseFinding package (11).

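### The stated 80% and 83% power hold only for fully observed data; the primary analysis also contains worst-case imputed values, for which Protocol 10.4 makes no visible allowance

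*Protocol*

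**What the plan says.** Protocol 10.4 sizes the trial in two steps. First, "To achieve at least 80% power for the multiple contrast test in the MCP-Mod approach under all different alternatives", it arrives at 288 patients (72 placebo, 24 at 5 mg, 48 at each other dose). Table 10-2 gives 80.31% for the linear shape at that size, the lowest of the five. Second, it states that 288 "is sufficient to reject at least one of the two primary efficacy hypotheses with a power of about 83" per cent under the Hochberg rule. The inputs are those of Protocol 10.3.2.2: "The measurements of the primary efficacy variables are assumed to be normally distributed with the same standard deviation", with SD 7 for LVEF and 0.85 for log NT-proBNP.

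To allow for losses, 384 patients are randomized, of whom about 75% "will contribute complete data to the primary analysis in the PPS".

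Protocol 10.3.3 then keeps some adherent patients in the per-protocol set although they have no Week 20 value, namely where the gap is "due to CV death or a hospitalization for HF preventing the assessment of the relevant efficacy endpoints 20 weeks after randomization". They receive a multiple (not fixed) of the worst change in their own treatment group. SAP 6.2.1.2 words the trigger differently: "For missing post-baseline value due to CV death or study drug/study discontinuation due to HF, a worst case approach (WOV) will be applied". It sets the value at 1.0 times the median, across arms, of each arm's worst change. A favourable group-worst value counts as 0, and LVEF has a floor. Both passages concern the primary analysis, not a sensitivity analysis.

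**The concern.** The analysis that was powered is not the analysis that will be run. The 25% allowance in 10.4 removes patients from the count. It does not cover patients who stay in the analysis with an extreme value. Those values do three things:

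- they shrink the dose contrast, because imputed patients carry no dose effect;
- they inflate the residual SD;
- they make the two endpoints correlated, because the same patient is usually extreme on both.

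All three lower the power for at least one rejection. The linear LVEF figure is 80.31% at N = 288, so there is almost no slack. A null result in this proof-of-concept and dose-finding trial would be read against 83%. If the real figure is in the 70s, that reading gives too much weight to a negative outcome.

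**Working it through.** **Inputs from the documents.** Group sizes 72/24/48/48/48/48; LVEF change 2 on placebo and 5 at maximum, SD 7; log NT-proBNP change -0.105 and -0.357, SD 0.85; the five shapes of Table 10-1; one-sided 5%; Hochberg at 5% and 2.5%; the SAP imputation rule.

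**Inputs assumed.** The share of imputed patients (the documents give none), equal shares across arms, and the LVEF/NT-proBNP correlation (not stated).

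**Step 1: reproduce the plan.** Optimal contrasts at these group sizes match SAP Table 6-2. The multivariate t critical values (282 df) are about 1.97 (5%) and 2.27 (2.5%). With nothing imputed, simulated LVEF power under the linear shape is 80.1-80.2% (stated 80.31%), and the other four shapes also agree with Table 10-2. Power for at least one endpoint is 83.3-83.4% with the linear shape and zero correlation. At correlation 0.3 it is 79.6%, and at 0.5 it is 77.1%. The stated 83% therefore corresponds to no imputed values and uncorrelated endpoints.

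**Step 2: size of the effect by hand (LVEF, linear shape, SAP rule).**
- Mean dose: (24×5 + 48×(10+20+30+40))/288 = 17.08 mg. Mean change: 2 + 0.075×17.08 = 3.28.
- The simulated imputed change is about -12, so it lies 15.28 points below the mean (squared: 233.5).
- With share p in every arm, the contrast shrinks by (1-p) and the variance becomes 49(1-p) + 233.5p(1-p).
- p = 3%: variance 47.53 + 6.79 = 54.32, SD 7.37; signal-to-noise factor 0.97×7/7.37 = 0.92.
- p = 5%: variance 46.55 + 11.09 = 57.64, SD 7.59; factor 0.95×7/7.59 = 0.88.

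A signal 8-12% weaker is enough to cost several points of power.

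**Step 3: patient-level simulation.** Linear shape, equal shares, zero correlation. Inside means that imputed patients are counted within the 288; on top means 288 complete patients plus the imputed ones. Power in %:

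| Share imputed | At least one, SAP rule, inside | At least one, SAP rule, on top | At least one, own-arm rule (multiple 1.0), inside | LVEF test at 5%, SAP rule, inside |
|---|---|---|---|---|
| 0% | 83.3 | 83.3 | 83.3 | 80.1 |
| 1.25% | 80.0 | – | – | 77.7 |
| 2% | 78.1 | – | – | 76.2 |
| 3% | 75.6 | 76.5 | 78.3 | 74.2 |
| 4% | 73.1 | 74.6 | 76.8 | 72.2 |
| 5% | 70.9 | 72.3 | 75.9 | 70.3 |

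A share of 1.25% is about 4 of 288 patients (0.0125×288 = 3.6). At 8% under the SAP rule, power for at least one endpoint is about 65% inside and 68% on top. The own-arm rule with imputed patients on top gives about 77-80% at 3-5%.

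**Step 4: other shapes.** At least one endpoint, SAP rule, inside, at 3 / 4 / 5%: sigmoidal Emax 1 88.5 / 86.5 / 84.7; Emax 84.9 / 82.8 / 80.7; sigmoidal Emax 2 83.3 / 81.1 / 78.9; quadratic 82.4 / 80.2 / 78.1.

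**Step 5: correlation.** At correlation 0.3 (linear, SAP rule, inside) power for at least one endpoint is 72.2% at 3% and 67.6% at 5%.

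The table leaves out the SAP's LVEF floor. With an assumed baseline LVEF of 28 (SD 7) and a 5% floor, results move by about 0-2 points.

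**The case against.** **The share is not in the documents.** This objection stands. A reader might derive a rate from Protocol 3.1, which says "HF carries a prognosis comparable to many forms of cancer with a 5-year survival rate of approximately 50" per cent and describes acute HF hospitalization "occurring annually in up to 30% of HF patients with NYHA class III and IV". At constant rates these give 1 - 0.5^(140/1826.25) = 5.2% deaths and 1 - 0.7^(140/365.25) = 12.8% hospitalizations in 20 weeks. But this is general epidemiology: death from any cause, and all hospitalizations in the sicker classes. The trial enrols NYHA II-IV and excludes life expectancy under 12 months. The imputed group is only adherent patients whose CV death or HF event prevents the Week 20 measurement. Getting from there to 3-5% needs further assumptions, so 3-5% is not the protocol's own figure.

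**The SAP rule costs more than the protocol's rule.** Also true. The SAP rule is the operative one, but the loss under the own-arm rule is smaller and should be shown next to it.

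**Linear is the worst shape.** True, and the other four hold at 3-4%. But 10.4 claims 80% under all alternatives, so the minimum is the right test of that claim.

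**The allowance may already be built in.** Section 10.4 says that its numbers include adequate assumptions on drop-out and missing data, and one could argue that SD 7 already describes the endpoint as analysed. Neither document says so. The normal model and the reference to complete data point the other way.

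**Equal shares may be wrong.** If the drug reduced these events, power would recover. A reader might infer that 83% requires an event reduction of about 45%. That figure needs both the SAP rule and imputed patients counted inside the 288. With them on top, about one third is enough, and under the own-arm rule about 30% or less. The documents assume no effect on these events in either direction.

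**Conclusion.** The concern holds as an unstated assumption, not as an arithmetic error: Table 10-2 and the 83% are correct for the data they describe. The primary analysis will contain worst-case values that those figures leave out, so the stated power is too high by an amount that depends on a share the plan never gives.

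For the linear shape with equal shares and zero correlation, power for at least one endpoint reaches 80% at about 1.25% imputed under the SAP rule. It is 75-76% at 3%, 71-72% at 5%, and about 65-80% over assumed shares of 2-8%. The own-arm rule gives about 76-80% at 3-5%. The direction and mechanism are firm; the size is conditional on the share, the rule, the correlation and the way the 288 are counted.

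A reader might also infer that the trial must enrol more patients. The documents do not support that: any larger N would follow from an assumed share, one rule and one shape, and would be out of proportion for a Phase II trial.

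**What to change.** Keep 384 randomized patients. Re-run the Protocol 10.4 simulation with the SAP 6.2.1.2 imputation rule and:

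- state a range of imputed shares with its source, equal across arms as the base case;
- state the LVEF/NT-proBNP correlation used;
- say whether the 288 patients with complete data include imputed ones;
- replace the 80% and 83% with the resulting power range, by shape.

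Because the two documents give different rules, show the own-arm rule as a comparison.

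The cost is one simulation re-run and revised text in 10.4. No patients are added. The downside is a less favourable stated power.
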